7.1 Primary Estimand, Intercurrent Events, and Estimation

Primary Objective and Population: The primary objective is to compare the efficacy of intranasal administration of twice-daily doses of 186 μg and 372 μg of OPN-375 (fluticasone propionate) with placebo in subjects with documented CRS with or without nasal polyps.

7.1.1 Co-primary Endpoints

1. Change from baseline to the end of Week 4 in the 7-day average AM, instantaneous CSNS; CSNS includes congestion, facial pain or pressure sensation, and nasal discharge (anterior and/or posterior). Further details on the daily nasal symptoms diary and the derivation of the CSNS and the 7-day average are provided in Section 9.3.1.

AND

2. The change from baseline to Week 24/ET in the APOV in the ethmoid and maxillary sinuses.

The APOV is the average percentage of volume opacified across both maxillary and ethmoid sinuses (all 4 sinuses). Further details on derivation of APOV is provided in Section 9.3.2.

7.1.2 Intercurrent Events

The potential intercurrent events are as follows:

1. Need for systemic corticosteroids for CRS exacerbation or worsening of CRS nasal/sinus symptoms
2. Need for nasal surgery; i.e., study discontinuation for nasal surgery
3. Discontinuation from study treatment

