#### **4.3 Withdrawal and Removal of Subjects**

Subjects will be informed that they are free to withdraw from study treatment and/or the study at any time at their own request without prejudice to their future medical care, or that they may be withdrawn at any time at the discretion of the investigator or Sponsor for safety, nonadherence to protocol requirements, or administrative reasons (eg, termination of study by Sponsor). Subjects wishing to withdraw from study treatment will be strongly encouraged to continue in the study and have all scheduled study procedures performed.

A subject must be withdrawn from treatment for the following reasons:

- subject becomes pregnant
- A subject's study treatment will be discontinued if the investigator or Sponsor considers it in the subject's best interest to stop treatment, (eg, for safety or significant tolerability reasons such as an AE). Subjects who have one of the following AEs must be withdrawn from study treatment.
  - IOP of >21 mm Hg
  - nasal septal perforation
  - new onset or worsening of cataract

A subject may also be withdrawn from study treatment for the following reasons:

- lack of efficacy
- protocol violation

A subject may be withdrawn from the study for the following reasons:

- withdrawal of consent
- adverse event
- protocol violation that makes it unsafe for the subject to continue in the study
- termination of the study

- lost to follow up
- public health measure
- other

If a subject withdraws from the study after starting study treatment, appropriate follow-up must be conducted wherever possible.

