#### **9.3.2 Potential Intercurrent Events**

The potential intercurrent events are as follows:

1. Need for systemic corticosteroids for CRS exacerbation or worsening of CRS nasal/sinus symptoms
2. Need for nasal surgery
3. Discontinuation from study treatment

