#### **9.3.3 Primary Estimand**

The primary efficacy estimand is the difference between each active treatment of twice-daily doses of 186 µg and 372 µg of OPN-375 and placebo for each of the co-primary endpoints.

For the primary estimand, intercurrent events will be addressed as follows:

1. Systemic corticosteroids use for CRS exacerbation or worsening of CRS nasal/sinus symptoms: a composite strategy will be employed with a poor score assigned to this event.
  - For CSNS, a value of '9' will be assigned. For APOV, a poor score is defined as follows: for a subject with a baseline APOV  $\geq 75\%$ , a value of '100%' is assigned; if baseline APOV  $< 75\%$ , a poor score is defined as baseline APOV + 25%. The rationale for assignment of a poor score is provided in the SAP. Also, further detail regarding the handling of a missing within-instrument data in these endpoints is provided in the SAP.
  - Systemic corticosteroid use for other indications will be considered a treatment and study discontinuation event (reference criteria 3).
2. Nasal surgery: composite strategy with poor scores assigned as above.
3. Treatment Discontinuation: treatment policy strategy; subjects may continue in the study until one of the following three mutually exclusive outcomes:
  - a. Subject completes Week 24/ET CT scan. In the absence of an intercurrent event (systemic corticosteroids, nasal surgery) use the endpoint value;
  - b. An intercurrent event (systemic corticosteroids for CRS exacerbation or worsening of CRS nasal/sinus symptoms, nasal surgery) occurs: Use composite strategy and assign poor score as described above (reference criteria 1,2);
  - c. Subject discontinues the study. Missing data due to study discontinuation following treatment discontinuation will be imputed; further detail on the imputation method is provided in the estimation section for each of the co-primary endpoints.

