2 INTRODUCTION

This Statistical Analysis Plan (SAP) has been developed after review of Sponsor Protocol OPN-FLU-CS-3205 (Amendment 6.0, dated 07 January 2022) and the corresponding electronic case report form (eCRF). This SAP describes the statistical methods to be used for the analysis and reporting of all efficacy and safety data collected during the conduct of Protocol OPN-FLU-CS-3205.

This SAP supersedes the statistical considerations identified in original Protocol OPN-FLU-CS-3205, as well as the SAP dated 19 April 2021, which is based on Protocol Amendment 4.1 and is the basis for the IASAP dated 8 June 2021. This SAP contains all changes incorporated into Protocol Amendment 6.0, and there are no deviations from this amendment presented in this SAP. If additional analyses are performed to supplement the planned analyses described in this SAP they will be identified as such in the Clinical Study Report (CSR).

This SAP is being written with consideration of the recommendations outlined in the following International Conference on Harmonization (ICH) Guidance for Industry documents:

- E9: Statistical Principles for Clinical Trials
- E9-R1 Addendum: Estimands and Sensitivity Analysis
- ICH E3: Structure and Content of Clinical Study Reports

This SAP also incorporates the recent FDA Guidance regarding the COVID-19 Public Health Emergency (PHE):

- FDA Guidance on the Conduct of Clinical Trials of Medical Products during COVID-19 Public Health Emergency: Guidance for Industry, Investigators, and Institutional Review Boards, (11 May 2020)

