7.1.3 Primary Estimand

The primary efficacy estimand is the difference between each active treatment of twice-daily doses of 186 μg and 372 μg of OPN-375 and placebo for each of the co-primary endpoints.

For the primary estimand, intercurrent events will be addressed as follows:

1. Systemic corticosteroids use for CRS exacerbation or worsening of CRS nasal/sinus symptoms: a composite strategy will be employed with a poor score assigned to this event.

For CSNS, a value of '9' will be assigned; further detail regarding the assignment of a worst score to the diary data are provided in Section 9.3.1. For APOV, a poor score is defined as follows: for a subject with a baseline APOV $\geq 75\%$, a value of '100%' is assigned; if baseline APOV $< 75\%$, a poor score is defined as baseline APOV + 25%.

The rationale for assignment of a poor score is provided in Section [7.1.4](#) below. Further detail regarding the handling of a missing POV in individual sinuses is provided in Section [9.3.2](#).

Systemic corticosteroid use for other indications will be considered a treatment and study discontinuation event (reference criteria 3c).

2. Nasal surgery: composite strategy with poor scores assigned as above.
3. Treatment Discontinuation: treatment policy strategy; subjects may continue in the study until one of the following three mutually exclusive outcomes:
 - a) Subject completes Week 24/ET CT scan. In the absence of an intercurrent event (systemic corticosteroids, nasal surgery) use the endpoint value;
 - b) An intercurrent event (systemic corticosteroids for CRS exacerbation or worsening of CRS nasal/sinus symptoms, nasal surgery) occurs: use composite strategy and assign poor score as described above (reference criteria 1, 2);
 - c) Subject discontinues the study. Missing data due to study discontinuation following treatment discontinuation will be imputed; further detail on the imputation method is provided in Section [7.1.5](#) for each of the co-primary endpoints.

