7.2 Sensitivity Analyses

7.2.1 Supplementary Estimand

A sensitivity analysis of the co-primary endpoints based on an alternative estimand will be performed.

Supplementary estimand: the difference between each active treatment of twice-daily doses of 186 µg and 372 µg of OPN-375 and placebo in each of the co-primary endpoints, irrespective of systemic corticosteroid use.

That is, for the supplementary estimand, intercurrent events will be addressed as follows:

1. Systemic corticosteroids use for all indications: treatment policy strategy; consider outcomes irrespective of systemic corticosteroid use; subjects may continue in the study until one of the following two mutually exclusive outcomes:
 - a) Subject completes Week 24/ET scan, use the endpoint value;
 - b) Subject discontinues the study. Missing data due to study discontinuation following treatment discontinuation will be imputed; further detail on the imputation method is provided in Section 7.1.5 for each of the co-primary endpoints.
2. Nasal surgery; i.e., study discontinuation for nasal surgery: composite strategy with poor scores assigned.
3. Treatment discontinuation: composite strategy with poor scores assigned.

For the supplementary estimand, the estimator and estimation methods for the co-primary endpoints, as well as the composite strategy with poor score assignments, are the same as for the primary estimand described above.

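### SAP 7.1.2 and 7.2.1 equate nasal surgery with leaving the study for it, which conflicts with the protocol and with SAP 7.1.3 and leaves a co-primary failure rule open to two readings

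*SAP*

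**What the plan says.** **Protocol.** Section 9.3.2 lists the second intercurrent event as "Need for nasal surgery". Section 9.3.3 handles it as "Nasal surgery: composite strategy with poor scores assigned as above", and Section 9.3.5 applies the same composite handling in the supplementary estimand. None of the three mentions leaving the study.

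**SAP, definition.** Section 7.1.2 writes the same event as "Need for nasal surgery; i.e., study discontinuation for nasal surgery".

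**SAP, primary estimand.** Section 7.1.3 item 2 repeats the protocol's handling sentence without the restriction. For subjects who stop treatment, item 3a says "In the absence of an intercurrent event (systemic corticosteroids, nasal surgery) use the endpoint value". Item 3b covers the case where "nasal surgery) occurs: use composite strategy and assign poor score as described above". Item 3c covers leaving the study, with missing values imputed. Section 7.1.4 then gives the poor score to events 1 and 2 as defined earlier in the text.

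**SAP, supplementary estimand.** Section 7.2.1 item 2 carries the restriction in the rule itself: "Nasal surgery; i.e., study discontinuation for nasal surgery: composite strategy with poor scores assigned". Item 3 gives a poor score to any treatment discontinuation.

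**Declared changes.** SAP Section 2 says "there are no deviations from this amendment presented in this SAP". Section 11 lists several changes made after Amendment 6.0, but not this one.

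**The concern.** The composite strategy exists so that a subject who resorts to surgery counts as a treatment failure. The CT taken after an operation should not stand as the result of the assigned arm. Making study exit part of the event opens a gap for anyone who has surgery and remains in follow-up.

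Such a subject is possible. Surgery is not a named reason for study withdrawal in Protocol 4.3. For those who stop study drug, the protocol says: "Subjects wishing to withdraw from study treatment will be strongly encouraged to continue in the study and have all scheduled study procedures performed".

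At stake is the scoring of these subjects on APOV and, if surgery falls before Week 4, on CSNS. The secondary endpoints whose intercurrent events SAP 7.3 and 7.5 refer back to 7.1.3 inherit the same uncertainty. If operations for uncontrolled disease were more frequent on placebo, using post-surgical values would shrink the treatment difference.

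**Working it through.** **1. Trace each type of operated subject through the rules.**

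| Subject | Protocol 9.3.3 / 9.3.5 | SAP 7.1.3 read literally | SAP 7.1.3 if the 7.1.2 definition governs | SAP 7.2.1 (supplementary) |
|---|---|---|---|---|
| A. Surgery, leaves the study for it | Poor score | Poor score (item 2) | Poor score, but item 3c describes the same act | Poor score |
| B. Surgery, stops drug, stays in study | Poor score | Poor score (items 2, 3b) | No surgery event; observed value via 3a | Poor score, through item 3 |
| C. Surgery, stays on drug and in study | Poor score | Poor score (item 2) | No event; observed value | No composite event; observed value |

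In the primary estimand, rows B and C depend on which section governs. In the supplementary estimand, only row C departs from the protocol.

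Row A shows a second problem. SAP 7.1.3 calls outcomes 3a to 3c mutually exclusive. If surgery means leaving the study for surgery, the subject who leaves meets 3b and 3c together. For APOV that is the poor score against jump-to-control imputation. For CSNS it is 9 against a missing-at-random estimate from the MMRM.

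**2. Reproduce the plan's design figure.** SAP 4.2 gives 111 per group, two-sided 5% and 88% power. With power = Φ(d / (s√(2/n)) − 1.96):

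- CSNS: d = 0.8, s = 1.9. The standard error is 1.9 × √(2/111) = 0.255, 0.8/0.255 = 3.137, and power is 88.0%.
- APOV: d = 11.3, s = 27. The standard error is 27 × √(2/111) = 3.624, 11.3/3.624 = 3.118, and power is 87.7%.

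Both agree with the stated 88%.

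**3. Illustrate what the two readings could move on APOV.** The poor score is baseline + 25 points when baseline is below 75% (SAP 7.1.3). The gap between the two scores for one subject is 25 minus the post-surgical change. The post-surgical changes and the counts below are assumptions, because the documents give neither. Shift in the arm difference = net excess of such subjects on placebo × gap / 111. The power column keeps SD = 27 and takes 11.3 as the difference under poor scoring.

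| Assumed post-surgical change | Gap | Shift, net excess 1 | Power | Shift, net excess 3 | Power |
|---|---|---|---|---|---|
| 0 | 25 | 0.23 | 86.3% | 0.68 | 83.4% |
| −20 | 45 | 0.41 | 85.2% | 1.22 | 79.5% |
| −40 | 65 | 0.59 | 84.0% | 1.76 | 75.0% |

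A more extreme case is baseline 65%, poor score 90% and post-surgical CT 20%. The gap is 70, and the shift is 70/111 = 0.63 for one subject or 1.89 for three. Against 11.3, three net subjects amount to 0.68/11.3 = 6% up to 1.89/11.3 = 17%.

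**The case against.** The strongest reply is that SAP 7.1.3 is the operative section and answers the question. Its item 2 matches Protocol 9.3.3. Item 3a bars the endpoint value after nasal surgery, and item 3b gives the poor score to a subject who stopped drug, remained and was operated on. The restricted phrase sits in a list of potential events. The backward reference in 7.1.4 could point to the numbered list in 7.1.3, which is closer. SAP 7.3.2 and 7.5.10 also name surgery and study discontinuation as separate events.

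Much of this stands. A reader might infer that the SAP scores operated subjects who stay on their post-surgical CT in the primary analysis. The documents do not support that as a statement of fact. It follows only if the 7.1.2 definition overrides the plain words of 7.1.3, and no passage says that it does. The observed-cases analysis in 7.2.3 does use observed values after intercurrent events, but by design.

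Two further inferences fail:

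- SAP 5.6 names sinus surgery as a possible reason for exclusion from the per-protocol set. This does not show that operated subjects remain in follow-up, because FAS membership rests on dosing, baseline data and an early CSNS value. Someone who left for surgery can be in the FAS.
- Protocol 4.3 does not encourage operated subjects as such to stay. It addresses those stopping study drug, does not mention surgery, and leaves an open category among the study-withdrawal reasons.

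Planned sinonasal surgery is an exclusion criterion, so counts may be small.

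The reply does not remove the conflict. Section 7.1.2 is where the event is defined, and 7.1.4 relies on a definition given earlier. The clause appears twice, and in 7.2.1 it is part of the rule.

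**Conclusion.** The point holds as an undeclared conflict of wording. SAP 7.1.2 and 7.2.1 depart from Protocol 9.3.2, 9.3.3 and 9.3.5, and 7.1.2 sits against SAP 7.1.3. For the primary estimand and the endpoints that follow 7.1.3, the result is ambiguity about subjects who have surgery and stay. For the supplementary estimand it is a real departure, limited to those who also stay on study drug.

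The size is unknown. At 111 per arm and an assumed gap of 25 to 70 points, each net excess placebo subject is worth about 0.2 to 0.6 APOV points. The dilution assumes more such subjects on placebo than on active; it would not favour the drug. The shifts are simple differences in arm means, and the ANCOVA adjustment could alter them somewhat. A co-primary failure rule should have one reading before unblinding, so the correction is worth making even if few subjects are affected.

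**What to change.** Remove the i.e. clause from the surgery event in SAP 7.1.2 and from item 2 of SAP 7.2.1. Then add one sentence, in line with the protocol: nasal or sinus surgery after randomisation and before the endpoint assessment in question (Week 4 for CSNS, the Week 24/ET CT for APOV) receives the poor score whether or not the subject remains in the study, and this takes precedence over imputation under item 3c.

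If the sponsor intends the narrower event, SAP 7.1.3 needs to be aligned with it, the change listed in Section 11 with a reason, and the Section 2 statement amended.

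The cost is one phrase in two places and one added sentence. No new data are needed, because the study schedule already collects procedures at every visit and subject contact.

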7.1.3 Primary Estimand

The primary efficacy estimand is the difference between each active treatment of twice-daily doses of 186 μg and 372 μg of OPN-375 and placebo for each of the co-primary endpoints.

For the primary estimand, intercurrent events will be addressed as follows:

1. Systemic corticosteroids use for CRS exacerbation or worsening of CRS nasal/sinus symptoms: a composite strategy will be employed with a poor score assigned to this event.

For CSNS, a value of '9' will be assigned; further detail regarding the assignment of a worst score to the diary data are provided in Section 9.3.1. For APOV, a poor score is defined as follows: for a subject with a baseline APOV $\geq 75\%$, a value of '100%' is assigned; if baseline APOV $< 75\%$, a poor score is defined as baseline APOV + 25%.

The rationale for assignment of a poor score is provided in Section [7.1.4](#) below. Further detail regarding the handling of a missing POV in individual sinuses is provided in Section [9.3.2](#).

Systemic corticosteroid use for other indications will be considered a treatment and study discontinuation event (reference criteria 3c).

2. Nasal surgery: composite strategy with poor scores assigned as above.
3. Treatment Discontinuation: treatment policy strategy; subjects may continue in the study until one of the following three mutually exclusive outcomes:
 - a) Subject completes Week 24/ET CT scan. In the absence of an intercurrent event (systemic corticosteroids, nasal surgery) use the endpoint value;
 - b) An intercurrent event (systemic corticosteroids for CRS exacerbation or worsening of CRS nasal/sinus symptoms, nasal surgery) occurs: use composite strategy and assign poor score as described above (reference criteria 1, 2);
 - c) Subject discontinues the study. Missing data due to study discontinuation following treatment discontinuation will be imputed; further detail on the imputation method is provided in Section [7.1.5](#) for each of the co-primary endpoints.

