3.0	
Synopsis: Updated for consistency with protocol
 
Schedule of Study Procedures and Evaluations:
 
 
Added “SARS-CoV-2 Serology Testing” to Visit 6 to determine if subject carries the antibodies
 
	15 June 2020

	

• Removed “X” from “Nasal Examination from Visit 3 and Visit 5”. Given the potential risks associated endoscopy and COVID-19 the frequency of these exams was reduced. Also, given the well-established safety profile of OPN-375, nasal examinations at the interim visits are not deemed necessary and efficacy measures are not required at interim timepoints.

• Removed “X” from “Nasal Polyp Grading from Visit 3 and Visit 5” and section 7.2 because nasal exams will not be required at these visits.

• Added abbreviation for “End of Study (EOS)” to be consistent in use of terminology

• Updated superscript comments to be consistent with protocol

 
Schedule of Study Procedures and Evaluations and Section 6.5:
 

• Added clarification to Visit 6 if subject cannot complete EOS CT scan at the Week 24 visit and continues treatment due to issues related to COVID-19 pandemic or due to any upper respiratory infection.

 
Section 1.3 Updated language to be more general and not specify countries
 
Section 3.1, 6.0 and 6.1
 

• Clarified timeline for CT completion at baseline.

 
Schedule of Study Procedures and Evaluations and Table 5;
 

• Removed “on site visit” and “office” to clarify urine pregnancy test must be completed at each visit

• Added a requirement for subjects who continue treatment past Week 24/Visit 6 to have an additional pregnancy test completed upon returning to site.

• Added “Blood Sample for SARS-CoV-2 serology testing” to Week 24/Visit 6 to determine if subject carries the antibodies

 
Synopsis and Section 4.1, (Inclusion Criterion 13)
 

• Removed “oral steroids” to address an inconsistency in protocol. Oral steroids are not allowed within 1 month of screening.

 
Synopsis and Section 4.2, (Exclusion Criteria 18)
 

• Revised to include “influenza, or SARS-CoV-2 (COVID-19)” to address new concerns related to COVID-19 pandemic.

 
Synopsis, Section 4.2, (Exclusion Criteria 34) and Section 5.6.3:
 

• Revised to include “cobicistat” to examples of cytochrome P450 3A4 inhibitors

 
Section 4.3
 

• Removed “receives systemic corticosteroids (oral or parenteral)” from reasons as subjects will no longer be withdrawn from the study per FDA request

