For the treatment policy estimand, (reference Section 7.1.3, criteria 3, c), missing data due to study discontinuation will be imputed with a pattern mixture model (PMM) multiple imputation (MI) using the Jump-to-Control (J2C) method. The PMM assumes that the missing data at Week 24/ET on the control arm (placebo) is MAR, and the missing data on the active treatment arms have the profile of the control arm at Week 24/ET.

Multiple imputation using a PMM with J2C method will be conducted using the sequential modeling method as described in (O'Kelly & Ratitch, 2014). Further detail on the MI implementation, and statistical analysis and inference is provided in Section 10.

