7.3.2 Acute CRS Exacerbations – Pooled Analysis

How an acute CRS exacerbation is defined and captured in this study is described in Section 9.3.5. The frequency of acute sinus exacerbations over 24 weeks will be compared between OPN-375

dose groups and placebo using generalized linear model (GLM) for data from the negative binomial distribution that is commonly referred to as the negative binomial (NB) regression model. The NB model will include the same model terms as the primary models; in addition, the model will include a categorical effect for protocol (CS-3205, CS-3206), and the logarithm of exposure time as an offset variable.

Regarding intercurrent events, use of systemic corticosteroids is included in the definition of acute exacerbation; subjects who have surgery or study discontinuation events will be censored at the time of the intercurrent event. Subjects who discontinue treatment are followed to study completion or intercurrent event as described in Section 7.1.3.

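### Systemic steroid use for a non-CRS reason is labelled a study discontinuation, yet the subject may stay, and no branch of the primary estimand says clearly whether the observed data count

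*SAP*

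**What the plan says.** The two documents share the operative sentence and differ in the cross-reference.

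- Protocol 9.3.3: "Systemic corticosteroid use for other indications will be considered a treatment and study discontinuation event (reference criteria 3".
- SAP 7.1.3: "Systemic corticosteroid use for other indications will be considered a treatment and study discontinuation event (reference criteria 3c".

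Criterion 3 is treatment discontinuation. It is declared to follow a treatment policy strategy, with three mutually exclusive outcomes that match in substance across the documents:

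- **3a**, the Week 24/ET CT is done: "In the absence of an intercurrent event (systemic corticosteroids, nasal surgery) use the endpoint value".
- **3b**, systemic steroids for CRS, or nasal surgery: a poor score is assigned.
- **3c**: "Subject discontinues the study. Missing data due to study discontinuation following treatment discontinuation will be imputed".

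Under 3c, APOV is multiply imputed by Jump-to-Control, so that "the missing data on the active treatment arms have the profile of the control arm at Week 24/ET" (SAP 7.1.5). Missing placebo APOV values are imputed under MAR, and CSNS is handled under MAR within the MMRM.

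The intercurrent event lists (Protocol 9.3.2, SAP 7.1.2) restrict the steroid event to CRS. None of the withdrawal lists in Protocol 4.3 names systemic steroid use, and the section adds: "Subjects wishing to withdraw from study treatment will be strongly encouraged to continue in the study and have all scheduled study procedures performed". For context, the version history entry for 3.0 says the steroid reason was taken out of Section 4.3 "as subjects will no longer be withdrawn from the study per FDA request".

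For the pooled exacerbation endpoint, SAP 7.3.2 says "subjects who have surgery or study discontinuation events will be censored at the time of the intercurrent event". SAP 9.3.5 computes follow-up time to the actual Week 24/ET visit date.

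**The concern.** Take a subject who has a short systemic steroid course in Week 5 for an asthma flare, stays in the study, and has the CT at Week 24, 19 weeks later. The analysis rules call this subject a study discontinuation, but the conduct rules do not require withdrawal. The plan must then say whether the CT counts, and it does not do so clearly.

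Three alpha-controlled quantities depend on the answer:

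- the APOV co-primary;
- the CSNS co-primary, if the course falls before about Day 28;
- the follow-up time and event count in the exacerbation analysis.

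SAP Section 10 aims at enough detail for an independent party to replicate the efficacy analysis. On this point two competent programmers could produce different values, and the choice could end up being made after unblinding.

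**Working it through.** **1. Walk the subject through criterion 3.** Assume non-CRS systemic steroid use, no surgery, still in the study, with Week 4 diary and Week 24 CT available.

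| Branch | Condition | Does the subject fit? |
|---|---|---|
| 3a | CT done, and no systemic corticosteroids or nasal surgery; no indication stated in the parenthesis | Not if the parenthesis is read literally. Yes if it means the listed intercurrent event, which is CRS use only |
| 3b | Systemic steroids for CRS, or nasal surgery | No |
| 3c | Subject leaves the study; missing data imputed | No: the subject has not left and the endpoint is not missing |

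The label and the SAP pointer send the subject to 3c by declaration. That has little purpose unless post-event values are set aside. Setting them aside is not treatment policy, which uses the outcome whatever the event. Yet 3c speaks only of missing data, and SAP 9.1.5 takes the latest available post-baseline value as Week 24/ET. Observed values are thus implied to be replaced but never stated to be.

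**2. Exacerbation rate.** If the steroid course is a study discontinuation event, SAP 7.3.2 stops the subject's follow-up on that date. SAP 9.3.5 runs it to the attended Week 24/ET visit. One subject then has two possible offsets and possibly two event counts.

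**3. The plan's own power figure.** Inputs from Protocol 9.1: 111 per group, two-sided 5%, CSNS difference 0.8 with SD 1.9, APOV difference 11.3 with SD 27.

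Power ≈ Φ(d / (SD × √(2/n)) − 1.96), with √(2/111) = 0.1342.

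- CSNS: 0.8 / (1.9 × 0.1342) = 3.137, giving 88.0%.
- APOV: 11.3 / (27 × 0.1342) = 3.118, giving 87.7%.

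The noncentral t gives 87.8% and 87.4%. The stated 88% is reproduced.

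**4. Illustrative size for APOV.** The documents give no rate of non-CRS steroid use, so the share f of active-arm subjects affected is an assumption. Suppose their own CTs would carry the full 11.3-point effect, Jump-to-Control gives them about zero effect, and the SD stays at 27. The expected difference is then 11.3 × (1 − f).

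| f | Difference (points) | Power | Loss (points) |
|---|---|---|---|
| 0% | 11.30 | 87.7% | – |
| 1% | 11.19 | 87.0% | about 0.7 |
| 3% | 10.96 | 85.6% | about 2 |
| 5% | 10.73 | 84.2% | about 3.5 |
| 10% | 10.17 | 80.1% | about 7.5 |

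No comparable figure was computed for CSNS or the exacerbation rate.

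**The case against.** A reader might infer that the protocol uses the observed CT for these subjects while the SAP discards it, so that the documents score the same subject differently. The text does not support that.

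- The protocol also calls the event a study discontinuation, and within criterion 3 that outcome is 3c. The SAP pointer can be read as a clarification, so its absence from the SAP Section 11 list of changes, and the SAP Section 2 statement of no deviations, are weak evidence of an undeclared change.
- Branch 3a is conditional on no systemic corticosteroids, so the protocol does not say that the CT is used.
- No passage sets an observed CT or diary score to missing.

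Nor does Protocol 4.3 keep these subjects in the study by name. They stay by omission and by a general encouragement aimed at those who wish to stop treatment. Systemic steroids are prohibited (Protocol 5.6.3), and Section 4.3 allows discretionary withdrawal for nonadherence or a protocol violation.

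It is also fair to say that other handling is already planned. The supplementary estimand applies treatment policy to steroids for all indications, the observed-cases analysis ignores intercurrent events, and the per-protocol set may exclude users of prohibited medication. None isolates this rule: the supplementary estimand also changes the handling of CRS steroid use and of treatment discontinuation, and observed cases changes the handling of every event.

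All of this stands, and it narrows the point to a missing rule. It does not supply the rule.

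**Conclusion.** The point holds as an unresolved rule for the primary estimand. Both documents label non-CRS systemic steroid use as leaving the study, Protocol 4.3 does not require it, and a subject who remains fits none of 3a to 3c cleanly. Following the SAP pointer implies replacing observed co-primary values, contrary to the declared treatment policy strategy. The exacerbation analysis has two conflicting end dates for the same subject.

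The size is modest unless the event is common: about 0.7 points of APOV power per 1% of active subjects affected, and about 7.5 points at 10%. This rests on an assumed event rate, on every affected CT carrying the full drug effect, and on no effect of the steroid course on the CT. In that illustration the APOV bias is toward the null, so no false-positive risk is shown. The main reason to act is that the values behind both co-primaries and one key secondary should be fixed before unblinding.

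**What to change.** These are changes to analysis wording only. Whether and when a subject should stop treatment after such a course is a clinical matter on which no view is taken here.

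1. In Protocol 9.3.3 and SAP 7.1.3, delete *and study discontinuation* and the 3/3c pointer. State instead: *for systemic corticosteroid use for non-CRS indications, observed endpoint values are used under treatment policy; imputation under 3c applies only if the subject actually leaves the study and the endpoint is missing.*
2. In 3a of both documents, limit the parenthesis to systemic corticosteroids for CRS, so that it agrees with 3b and the intercurrent event list. Without this, step 1 would contradict 3a.
3. In SAP 7.3.2, state that censoring applies only to actual study discontinuation, consistent with the follow-up time in SAP 9.3.5.
4. Keep the 3c handling of these subjects as a sensitivity analysis, stating explicitly that post-event values are set to missing in it.

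The cost is a few sentences in each document before unblinding, and no new data. The downside is that some observed values may carry an effect of the steroid course itself. The sensitivity analysis in step 4 would show how much this matters.
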